6. RANDOMISATION AND BLINDING

6.1 Randomisation

No randomisation is required as this is an observational study.

6.2 Blinding and Allocation Concealment

Results of group allocation (hyper/hypo) will be blinded to clinical and research staff.

7. ANALYSIS PRINCIPLES

Baseline characteristics, and follow-up measurements will be described using the appropriate descriptive summary measures depending on the scale of measurement.

Analyses will be performed using the software STATA version 15.1. (StataCorp LLC, College Station, Texas) and R version 4.3.1 (R Foundation for Statistical Computing, Vienna, Austria). Latent class analysis will be performed with Mplus version 8.8 (Muthen & Muthen, Los Angeles, California).

7.1 Primary Outcome

For the primary outcome of 60 day mortality, analysis will be conducted using the phenotype allocation defined by the POC assay. Absolute number and percentage by phenotype, unadjusted percentage point difference (95% confidence interval, CI) and risk ratio (95% CI) will be calculated.

Pearson's chi-square test will be used to compare the two phenotypes and p value will be reported.

7.2 Secondary Outcomes

A secondary analysis for the outcome of 60 day mortality using logistic regression to adjust for important variables (age, site, and gender) will be carried out. Odds ratio (95% CI) and p value will be reported.

Differences in 60 day mortality will also be evaluated using phenotype allocation as defined by i) commercially available assays in conjunction with a parsimonious logistic regression model and ii) LCA. For each i) and ii), analyses will be conducted by calculating: a) absolute number and percentage by phenotype, b) unadjusted percentage point difference (95%, CI), c) risk ratio (95% CI), and d) p value from Pearson's chi-square test (95% CI).

Further secondary outcomes will be analysed using both POC-derived phenotype allocation and LCA-derived phenotype allocation.

For secondary outcomes based on dichotomous variables (Re-intubation rate, 28-day mortality), absolute number and percentage by phenotype will be calculated, and p-value will be from Pearson's chi-square test.

For continuous secondary outcomes (Ventilator free days at day 28; Duration of ventilation; Length of ICU stay; Length of hospital stay), data will be reported as median (IQR) with p value derived from Mann-Whitney U test.

Analyses will be conducted to assess agreement of phenotype classification methods. Comparisons will be made between: (i) POC-derived phenotype versus phenotype from commercially available assays (defined by up to 8 different parsimonious logistic regression models [5]), (ii) POC-derived phenotype versus LCA-derived phenotype, and (iii) POC-derived phenotype versus phenotype derived from clinical classifier machine learning algorithm [11]. Cohen's kappa coefficient (95% CI) will be calculated and p-value will be from McNemar's test for agreement. All of these analyses will be performed for phenotype allocation at day 0 and at day 3. For additional comparisons between classification methods, LCA phenotype will be selected as the "gold standard" and sensitivity, specificity, negative predictive value, and positive predictive value will be calculated for all other methods. Area under the receiver operating curve (AUC) will also be calculated. These analyses will also be performed for phenotype allocation at day 0 and day 3.

Agreement of phenotype classification will also be assessed between day 0 and day 3 of study enrolment using POC-derived phenotype at day 0 and day 3, calculation Cohen's kappa coefficient (95% CI) and p-value from McNemar's test for agreement.

Stability of phenotype allocation over day 0 to day 3 and transition between phenotypes will be assessed by latent transition analysis (LTA).

The probabilities of phenotype allocation generated by parsimonious logistic regression models will be compared between those generated using data derived from POC assays to those generated using commercially available research-grade assays[5]. Comparisons will be made using Bland-Altman plots for the probabilities and McNemar's test for phenotype allocation using a probability cut-off of 0.5 to assign phenotypes.

For secondary outcomes related to feasibility of delivering a POC assay in NHS/HSE intensive care setting, assay technical failure rate will be calculated as absolute number and percentage of events. No inferential statistical analysis will be conducted.

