5. SAMPLE SIZE CALCULATIONS

Data from several retrospective analyses have shown that the percentage of patients with ARDS in the hyper-inflammatory sub-group was 27-34% of the overall population, that the mortality in the hypo-inflammatory sub-group was 17-23%, with a mortality difference between the hyper-inflammatory and hypo-inflammatory sub-groups ranging from 15-32%. A conservative percentage of patients in the hyper-inflammatory sub-group of 25%, a mortality in the hypo-inflammatory sub-group of 17% and a difference in 28-day mortality between the hyper-inflammatory and hypo-inflammatory sub-groups of 15% was assumed. The mortality in the hyper-inflammatory group is assumed to be 17% under the null hypothesis and 32% under the alternative hypothesis [7-10].

Based on a two group chi-square test, group sizes of 347 in the hypo-inflammatory group and 116 in the hyper-inflammatory group achieves 90% power at a two-sided significance level of 0.05 to detect a mortality difference between the groups of 15%. Based on our previous experience the group sizes

have been inflated by 10% to allow for technical failure, drop-out or loss to follow-up giving group sizes of 386 in the hypo-inflammatory group and 129 in the hyper-inflammatory group. As such, at least 515 patients with ARDS will be recruited.

An additional exploratory cohort of patients with COVID-19 will be recruited. No formal sample size calculation for this cohort is feasible. An indicative sample of up to 100 patients will be recruited in this cohort during the course of the study, however it is recognized that this is an estimate which will be dependent on the duration of the COVID-19 pandemic.

A further exploratory cohort of up to 300 patients with AHRF will be recruited. No formal sample size calculation for this cohort is feasible as these subphenotypes have not been described in such AHRF patients before. A sample of 300 patients is required in order to provide a minimum sample to undertake latent class analysis.

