- Intubation rate in patients receiving HFNO, percentage point difference/ RR adjusted for age, co-morbidity, aetiology of ARDS, vasopressor requirement and PF ratio. P-values will be from log binomial regression.
- Re-intubation rate, percentage point difference/ RR adjusted for age, co-morbidity, aetiology of ARDS, vasopressor requirement and PF ratio. P-values will be from log binomial regression.
- Ventilator free days at day 28, difference in means (95% CI) adjusted for age, co-morbidity, aetiology of ARDS, vasopressor requirement and PF ratio. P-values will be from ancova

- Duration of ventilation, difference in means (95% CI) adjusted for age, co-morbidity, aetiology of ARDS, vasopressor requirement and PF ratio. P-values will be from ancova.
- 28-day mortality, percentage point difference/RR adjusted for age, co-morbidity, aetiology of ARDS, vasopressor requirement and PF ratio. P-values will be from log binomial regression.

Agreement of phenotype classification:

- Agreement of phenotype classification using POC-derived phenotype versus phenotype from commercially available assays (defined by up to 8 different parsimonious logistic regression models [5]), Cohen's kappa coefficient and p value from McNemars test
- Agreement of phenotype classification using POC-derived phenotype and LCA-derived phenotype, Cohen's kappa coefficient and p value from McNemars test
- Agreement of phenotype classification using POC-derived phenotype and phenotype from clinical classifier machine learning algorithm [11], Cohen's kappa coefficient and p value from McNemars test
- Agreement of phenotype classification between baseline and day 3, by (i) latent transition analysis (LTA) and (ii) POC-derived phenotype at day 0 and day 3, reporting Cohen's kappa coefficient and p value from McNemars test
- Probability of phenotype allocation generated by POC-derived classifier versus phenotype from commercially available assays and parsimonious logistic regression models [5]. Comparisons will be made using Bland-Altman plots

Feasibility outcomes:

Feasibility of delivering a POC assay in NHS/HSE intensive care setting as measured by assay technical failure rate, reported as absolute number and percentage of events. No inferential statistical analysis will be conducted.

Sensitivity analysis:

The primary outcome, secondary analyses of the primary outcome, and secondary outcomes (when pertinent) will be analysed as above for the following subgroups:

- AHRF cohort

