Agreement of phenotype classification using a POC assay and commercially-available assay (model 3) [11]	N agreed= N disagreed=	N agreed= N disagreed=		
Agreement of phenotype classification using a POC assay and commercially-available assay (model 4) [11]	N agreed= N disagreed=	N agreed= N disagreed=		
Agreement of phenotype classification using a POC assay and commercially-available assay (model 5) [11]	N agreed= N disagreed=	N agreed= N disagreed=		
Agreement of phenotype classification using a POC assay and commercially-available assay (model 6) [11]	N agreed= N disagreed=	N agreed= N disagreed=		
Agreement of phenotype classification using a POC assay and commercially-available assay (model 7) [11]	N agreed= N disagreed=	N agreed= N disagreed=		
Agreement of phenotype classification using a POC assay and commercially-available assay (model 8) [11]	N agreed= N disagreed=	N agreed= N disagreed=		
Agreement of phenotype classification using a POC-derived phenotype and LCA-derived phenotype	N agreed= N disagreed=	N agreed= N disagreed=		
Agreement of phenotype classification between day 1 and 3	N agreed= N disagreed=	N agreed= N disagreed=		

^a p-value from McNemar's test used for agreement.

Table x.x.x Sensitivity analysis of the main clinical outcomes in patients with AHRF

	Hyper-inflammatory phenotype n = (%)	Hypo-inflammatory phenotype n = (%)	Unadjusted % Point or Mean Difference (95% CI)	Unadjusted risk ratio (95% CI)	p-value	Adjusted odds ratio (95% CI)	p-value
Primary outcome ^a							
Mortality at 60 days in patients with ARDS as defined by the POC assay							
Alive	N (xx.x%)	N (xx.x%)	xx.x (xx.x to xx.x)				
Dead	N (xx.x%)	N (xx.x%)	xx.x (xx.x to xx.x)	xx.x (xx.x to xx.x)	x.xxx		
Secondary outcomes							
Adjusted 60-day mortality (phenotype defined by POC assay)						xx.x (xx.x to xx.x)	x.xxx
Time to extubation ^b	xx.x (xx.x)	xx.x (xx.x)	xx.x (xx.x to xx.x)		x.xxx		x.xxx
Intubation rate^a	N (xx.x%)	N (xx.x%)	xx.x (xx.x to xx.x)		x.xxx		x.xxx
Re-intubation rate ^a	N (xx.x%)	N (xx.x%)	xx.x (xx.x to xx.x)		x.xxx		x.xxx
Ventilator free days at day 28 ^b	xx.x (xx.x)	xx.x (xx.x)	xx.x (xx.x to xx.x)		x.xxx		x.xxx
Duration of ventilation ^b	xx.x (xx.x)	xx.x (xx.x)	xx.x (xx.x to xx.x)		x.xxx		x.xxx
Length of ICU stay ^c	xx.x [xx.x, xx.x]	xx.x [xx.x, xx.x]			x.xxx		
Length of hospital stay ^c	xx.x [xx.x, xx.x]	xx.x [xx.x, xx.x]			x.xxx		
28-day mortality ^a							
Alive	N (xx.x%)	N (xx.x%)	xx.x (xx.x to xx.x)				

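### McNemar's test is reported as the p-value for agreement, but it tests only whether the two classifications call the same proportion hyper-inflammatory

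*Supplement*

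**What the plan says.** Section 7.2 sets out three between-method comparisons: the point-of-care (POC) phenotype against the commercial assays (up to 8 parsimonious models), against LCA, and against the clinical classifier. Each is done at day 0 and at day 3. For all of them, "Cohen's kappa coefficient (95% CI) will be calculated and p-value will be from McNemar's test for agreement". For stability between day 0 and day 3 the same section specifies "calculation Cohen's kappa coefficient (95% CI) and p-value from McNemar's test for agreement".

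Section 8.5 repeats the pairing for each comparison, for example "Agreement of phenotype classification using POC-derived phenotype and LCA-derived phenotype, Cohen's kappa coefficient and p value from McNemars test"; it does not restate the confidence interval for kappa. The agreement table in Appendix 1 has one p-value column, footnoted "p-value from McNemar's test used for agreement".

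Taken literally, this gives up to (8 + 1 + 1) x 2 + 1 = 21 p-values offered as evidence on agreement. Nowhere does the SAP say that the test addresses marginal proportions only.

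Section 7.2 also plans sensitivity, specificity, predictive values and AUC against LCA, latent transition analysis for stability, and Bland-Altman plots of the allocation probabilities. It makes one further use of McNemar's test, on allocation at a probability cut-off of 0.5, without attaching the words about agreement.

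**The concern.** Agreement means that the same patient receives the same label from both methods. The evidence for it is the share of patients in the two concordant cells. McNemar's statistic does not use those cells: it tests whether the discordant cells b and c are equal, which is the same as testing whether the two margins are equal. The p-value printed beside kappa therefore answers a different question.

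Agreement between POC and LCA is secondary objective (i), stability is secondary objective (ii), and agreement appears as secondary outcomes (ii) to (iv) in section 2.2. McNemar's test is the only hypothesis test that the plan names for agreement. A reader of the Appendix table could take a large p-value as support for agreement, or a small one as evidence against it, and neither follows. For day 0 against day 3, equal flows in both directions are real instability, yet they give p = 1.

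**Working it through.** **Inputs from the plan (section 5).** The calculation uses "group sizes of 347 in the hypo-inflammatory group and 116 in the hyper-inflammatory group achieves 90% power at a two-sided significance level of 0.05", with 25% hyper-inflammatory. It matters here only because it supplies realistic 2x2 margins.

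**Reproducing the plan's own figures.** Mortality is 17% against 32%.
- Pooled proportion: (347 x 0.17 + 116 x 0.32)/463 = 0.2076.
- SE under the null: sqrt[0.2076 x 0.7924 x (1/347 + 1/116)] = 0.0435.
- SE under the alternative: sqrt[0.17 x 0.83/347 + 0.32 x 0.68/116] = 0.0478.
- Power: Phi[(0.15 - 1.96 x 0.0435)/0.0478] = 91.2%, against the stated 90%.
- Inflation: 347/0.9 = 386, 116/0.9 = 129, 463/0.9 = 515, all as stated.

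So N = 515 with 129 hyper-inflammatory (25%) is a fair base. N = 463 with 116 is the analysable number after losses.

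**Assumed inputs.** The documents give no discordant counts. Those below are illustrations chosen to span poor to excellent agreement.

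**Formulas.** Cells are a (both hyper), b and c (discordant), d (both hypo), with total N.
- Observed agreement: Po = (a + d)/N.
- Chance agreement: Pe = [(a+b)(a+c) + (c+d)(b+d)]/N².
- Kappa: (Po - Pe)/(1 - Pe).
- McNemar chi-square on 1 df: (b - c)²/(b + c). Exact form: two-sided binomial on b and c with probability 1/2.

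The margins (a + b) and (a + c) are equal exactly when b = c. If both methods call the same number hyper-inflammatory, the statistic is therefore 0 and p = 1.00 whatever the agreement. A small p-value requires unequal margins.

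**Chance-level classification, N = 515, cells 32/97/97/289.**
- Independence predicts a = 129 x 129/515 = 32.3, so this is essentially two unrelated labels.
- Po = 321/515 = 0.623. Pe = (129² + 386²)/515² = 0.625. Kappa = -0.003 (95% CI -0.089 to 0.083).
- McNemar: (97 - 97)²/194 = 0, p = 1.00.
- Only 32/129 = 24.8% of one method's hyper-inflammatory patients are hyper-inflammatory by the other.

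**Near-perfect classification with a small one-sided shift, N = 515, cells 118/11/1/385 (margins 129 and 119).**
- Po = 503/515 = 0.977. Pe = (129 x 119 + 386 x 396)/515² = 0.634. Kappa = 0.936.
- McNemar: (11 - 1)²/12 = 8.33, p = 0.0039. Exact: 2 x (1 + 12)/2¹² = 0.0063. Continuity-corrected: 9²/12 = 6.75, p = 0.0094.

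**Other assumed tables.**

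| N | a / b / c / d | Agreement | Kappa | McNemar p |
|---|---|---|---|---|
| 515 | 69 / 60 / 60 / 326 | 76.7% | 0.379 | 1.00 |
| 463 | 29 / 87 / 87 / 260 | 62.4% | -0.001 (-0.092 to 0.090) | 1.00 |
| 463 | 0 / 116 / 116 / 231 | 49.9% | -0.33 | 1.00 |
| 463 | 116 / 0 / 0 / 347 | 100% | 1 | 1.00 by convention |
| 463 | 116 / 8 / 0 / 339 | 98.3% | 0.955 (0.924 to 0.986) | 0.0047; exact 0.0078; corrected 0.013 |

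At N = 463, total agreement, chance-level labels and no shared hyper-inflammatory patient at all give the same p-value. Kappa with its interval separates them clearly.

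**The case against.** The strongest reply is that agreement does not rest on this p-value. The sentence that names McNemar's test puts kappa with a 95% CI first. The Appendix table shows kappa with its CI and the counts agreed and disagreed in the same row, so in both main examples the reader would see kappa near 0 or 0.94 beside the p-value. Objective (i) also has sensitivity, specificity, predictive values and AUC against LCA. Stability also has latent transition analysis. All of this stands, and it sets the size of the point.

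It is also true that McNemar's test is a sound companion analysis. A tendency of the POC assay to over-call or under-call the hyper-inflammatory phenotype is worth knowing, and kappa does not isolate it. The fault lies in the label and the reading that the label invites.

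A reader might infer that the study will declare agreement whenever p exceeds 0.05, or reject a good assay when p is small. The documents do not support that: they attach no threshold, hypothesis or success criterion to the agreement outcomes. A reader might also infer that the stability objective is decided by McNemar's test; latent transition analysis is named for that purpose.

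What the reply does not remove is the label. Three places in the SAP call the result a p-value for agreement, section 8.5 pairs it with kappa without qualification, and no other text corrects it.

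**Conclusion.** The point holds as an error of label and interpretation in secondary analyses. As specified, the McNemar p-value carries no information on whether the same patients are classified alike: under the assumed counts at N = 515 it is 1.00 with kappa about 0, and 0.004 (exact 0.006) with kappa 0.94. The pattern is the same at N = 463, and the choice of exact, uncorrected or corrected form does not alter it. The particular figures depend on discordant counts that the documents do not give. The conclusion does not, because the statistic omits the concordant cells by construction.

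The reach is limited. The kappa estimates, the accuracy measures, the sample size and the primary comparison of 60-day mortality are untouched, and no decision rule hangs on the p-value. It should be fixed, but it does not threaten the study's main conclusion.

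**What to change.** In section 7.2 (between methods, and day 0 against day 3), section 8.5 and the Appendix 1 agreement table, do one of two things:
- remove McNemar's test as the p-value for agreement; or
- keep it, relabelled as a *test for systematic difference in the proportion called hyper-inflammatory*.

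In either case, add a sentence saying that conclusions on agreement rest on Cohen's kappa with its 95% CI, supported by positive and negative percent agreement, and restate the CI in section 8.5. For comparisons against LCA, the planned sensitivity and specificity already supply the percent agreements. For the rows in the Appendix table, they can be derived from the counts already planned. No kappa threshold is needed, since the study claims no success criterion for agreement and the documents offer no basis for one.

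The cost is a few sentences and one column heading with its footnote. No new data are needed, and no estimate changes.

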7.3 Sensitivity analysis

Primary and secondary outcomes (except those related to agreement between phenotype allocation and those related to feasibility) will be analysed and reported separately (when pertinent) for:

- AHRF cohort
- patients receiving mechanical ventilation
- patients receiving non-invasive ventilation
- patients receiving high-flow nasal oxygen
- patients receiving high-flow nasal oxygen with a flow rate of at least 30 litres per minute
- analysis excluding COVID-19 patients
- analysis restricted to patients with biosamples obtained within 24h of ARDS diagnosis
- analysis restricted to patients with biosamples obtained within 48h of ARDS diagnosis

7.4 Additional analysis

To study the performance of the New Global Definition of ARDS [12], primary and secondary outcomes will be reported for the entire study cohort, the study cohort stratified by ARDS severity as defined by the New Global Definition of ARDS [12], and the study cohort stratified by ARDS severity as defined by the Berlin Definition of ARDS [6].

An additional analysis will be conducted on the cohort of patients with AHRF, to assess the proportion of patients developing ARDS by phenotype. This will be reported as absolute number and percentage, with p value for difference between phenotypes from Fisher's exact test. In AHRF developing ARDS, the median (IQR) number of days to ARDS development will be calculated by phenotype, with p value for difference between phenotypes from Mann Whitney U test.

Outcomes will be compared within a given phenotype with respect to ARDS/AHRF diagnosis. Primary and secondary outcomes will be compared for all hyperinflammatory patients (ARDS vs. AHRF) and all hypoinflammatory patients (ARDS vs. AHRF). Comparisons will be made using Fisher's exact test for categorical outcomes and Mann-Whitney U Test for continuous outcomes.

Subsequent analyses after study completion may explore the relationship between hyperinflammatory and hypoinflammatory phenotypes and other ARDS phenotypes [13] and sepsis phenotypes [14,15] as well as the use of varying probability cutpoints for phenotype assignment in comparison to full latent class analysis.

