1. BACKGROUND AND DESIGN

Full details of the background to the study and its design are presented in the protocol.

The hypothesis that is under investigation is that patients prospectively classified to the hyper-inflammatory ARDS phenotype on the basis of clinical characteristics and a novel POC biomarker assay will have worse clinical outcomes than the hypo-inflammatory phenotype.

Aim:

The purpose of this project is to prospectively identify hyper- and hypo-inflammatory phenotypes in patients with ARDS and AHRF, and determine clinical outcomes associated with each phenotype.

Objectives:

Primary:

(i) Assess the clinical outcomes in patients with ARDS according to their prospectively defined inflammatory phenotype determined using a POC assay.

Secondary:

- (i) Assess the agreement of the phenotype allocation using a POC assay and latent class analysis (LCA) from biomarkers and the clinical study dataset
- (ii) Assess the stability of phenotype allocation over time
- (iii) Feasibility of delivering a POC assay in the NHS intensive care setting
- (iv) Identify if inflammatory phenotypes are present and influence outcomes in patients with AHRF

Patients will be eligible for the study if they meet the inclusion criteria.

Inclusion criteria

1. Patient is receiving mechanical ventilation, CPAP or high flow nasal oxygen (HFNO)
 2. a) ARDS as defined by the Berlin definition [6]
 - Onset within 1 week of identified insult
 - Within the same 24-hour time period:
 - i. Hypoxaemic respiratory failure ($\text{PaO}_2/\text{FiO}_2$ ratio $\leq 40\text{kPa}$ on $\text{PEEP} \geq 5\text{ cmH}_2\text{O}^*$)
 - ii. Bilateral infiltrates consistent with pulmonary oedema not explained by another pulmonary pathology
 - iii. Respiratory failure not fully explained by cardiac failure or fluid overload
- OR
- b) AHRF as defined by
 - Within the same 24-hour time period:
 - i. Hypoxaemic respiratory failure ($\text{PaO}_2/\text{FiO}_2$ ratio $\leq 40\text{kPa}$ on $\text{PEEP} \geq 5\text{ cmH}_2\text{O}^*$)

- ii. Unilateral infiltrates on chest imaging not fully explained by effusions, collapse, or nodules
- iii. Respiratory failure not fully explained by cardiac failure or fluid overload

The time of onset of ARDS is when the last ARDS criterion is met.

*PEEP assumed ≥ 5 cmH₂O if on HFNO

[figure not shown]
Patients will not be eligible for the study if they meet any of the exclusion criteria.

Exclusion criteria

1. Age <18 years of age

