2. OUTCOME MEASURES

2.1 Primary outcome measure(s)

The primary outcome is mortality at 60 days in the hyper-inflammatory and hypo-inflammatory phenotypes in patients with ARDS.

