- patients receiving mechanical ventilation
- patients receiving non-invasive ventilation
- patients receiving high flow nasal oxygen
- patients receiving high-flow nasal oxygen with a flow rate of at least 30 litres per minute
- analysis excluding COVID-19 patients
- analysis restricted to patients with biosamples obtained within 24h of ARDS diagnosis
- analysis restricted to patients with biosamples obtained within 48h of ARDS diagnosis

Additional analysis

- Primary and secondary outcomes for the total cohort
- Primary and secondary outcomes for the total cohort, stratified by severity as defined by the New Global Definition of ARDS [12]
- Primary and secondary outcomes for the total cohort, stratified by severity as defined by the Berlin Definition of ARDS [6]
- ARDS development among patients with AHRF, absolute number and percentage. Comparisons made stratified on phenotype allocation.
- Time to ARDS development in patients with AHRF developing ARDS, median (IQR) number of days. Comparisons made stratified on phenotype allocation.
- Primary and secondary outcomes within each phenotype with respect to ARDS/AHRF diagnosis
- Comparison of hyperinflammatory and hypoinflammatory phenotypes to other ARDS phenotypes [13]
- Comparison of hyperinflammatory and hypoinflammatory phenotypes to sepsis phenotypes [14,15]
- The use of varying probability cutpoints for phenotype assignment in comparison to full latent class analysis

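### The additional analysis meant to study the New Global Definition's performance plans parallel outcome tables by New Global and Berlin severity, with no cross-classification, discrimination measure or paired contrast between them

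*Supplement*

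**What the plan says.** The first paragraph of SAP section 7.4 opens with a purpose: "To study the performance of the New Global Definition of ARDS [12], primary and secondary outcomes will be reported for the entire study cohort". Two further displays follow. One is "the study cohort stratified by ARDS severity as defined by the New Global Definition of ARDS [12"; the other repeats that display with the older grading, namely "the study cohort stratified by ARDS severity as defined by the Berlin Definition of ARDS [6". The list under Additional analysis in section 8.5 matches. After outcomes for the total cohort it has "Primary and secondary outcomes for the total cohort, stratified by severity as defined by the New Global Definition of ARDS [12"; its next line does the same for the older grading, namely "Primary and secondary outcomes for the total cohort, stratified by severity as defined by the Berlin Definition of ARDS [6". Neither section gives a statistic, an effect measure or a contrast between the definitions.

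Three other places bear on this:

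- Section 2.1 ties the primary outcome to the phenotypes: "The primary outcome is mortality at 60 days in the hyper-inflammatory and hypo-inflammatory phenotypes in patients with ARDS".
- The inclusion criteria in section 1 admit patients by one of two routes. One is "ARDS as defined by the Berlin definition [6", with PEEP assumed to be at least 5 cmH2O on high-flow nasal oxygen (HFNO). The other is AHRF with unilateral infiltrates.
- Later in section 7.4, for ARDS against AHRF within a phenotype, a method is named: "Comparisons will be made using Fisher's exact test for categorical outcomes and Mann-Whitney U Test for continuous outcomes".

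**The concern.** The purpose clause asks how a definition performs. The planned output shows what happened to patients under each of two gradings, side by side. To judge one grading against the other, a reader needs to know which patients change category, what happened to those patients, and whether one grading separates deaths better than the other. None of the three is planned.

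As written, a later statement that the new definition grades risk better than, worse than or the same as Berlin would have one of two bases. It could come from comparing by eye two sets of percentages that share most of their patients, or from a measure chosen after the data were seen. Separate confidence intervals would not help, because they ignore the pairing.

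**Working it through.** **Is the comparison specified elsewhere in the SAP?**

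- Section 7.2 names kappa, McNemar's test, sensitivity, specificity, predictive values, AUC and Bland-Altman plots. All are for phenotype classification methods, and so is the agreement list in section 8.5.
- Section 7.3 plans separate analyses for HFNO and for HFNO at 30 L/min or more. It does not link them to a comparison of definitions.
- The tests in the rest of section 7.4 cover progression from AHRF to ARDS, and ARDS against AHRF within a phenotype.
- Appendix 1 has table shells for each sensitivity cohort and none for the New Global or Berlin strata.

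The comparison is therefore not specified. The SAP also does not say how AHRF patients, who belong to the entire cohort, are placed in ARDS severity strata.

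**What pairing would buy (illustration).** The SAP gives no figure to reproduce here. Only the 515 ARDS patients come from it (section 5). The rest is assumed: three grades holding 25/45/30% of patients; 60-day mortality of 13/19/30% by Berlin grade; and a second grading equal to the first except that a random share r of patients is re-drawn from the same 25/45/30% split.

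1. Overall mortality = 0.25×0.13 + 0.45×0.19 + 0.30×0.30 = 0.208.
2. Grade split among deaths = 0.0325, 0.0855 and 0.0900, each over 0.208 = 0.156, 0.411, 0.433. Among survivors = 0.2175, 0.3645 and 0.2100, each over 0.792 = 0.275, 0.460, 0.265.
3. C = P(death has the higher grade) + ½P(tie) = 0.156×½×0.275 + 0.411×(0.275 + ½×0.460) + 0.433×(0.275 + 0.460 + ½×0.265) ≈ 0.604.
4. A random re-draw shrinks the excess over 0.5 by (1−r). With r = 0.20, C = 0.5 + 0.8×0.104 = 0.583, a loss of 0.021. With r = 0.10 the loss is 0.010.
5. Same-grade share = (1−r) + r×(0.25² + 0.45² + 0.30²) = (1−r) + 0.355r. This is 87% at r = 0.20 and 94% at r = 0.10.
6. In 3,000 simulated cohorts of 515, each C-statistic has SE about 0.028, so its own 95% CI is ±1.96×0.028 = ±0.055. Treated as independent, the difference has SE √2×0.028 = 0.040.
7. The results for the paired difference are below. Power is Φ(loss/SE − 1.96).

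| Same grade | Loss in C | Paired SE | 0.040 / paired SE | 95% half-width | Power |
|---|---|---|---|---|---|
| 94% | 0.010 | 0.013 | 3.1 | 0.025 | Φ(0.77−1.96) = 12% |
| 87% | 0.021 | 0.018 | 2.2 | 0.035 | Φ(1.17−1.96) = 21% |

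Pairing is clearly more precise, but a difference near 0.02 would usually be missed. The value of the paired estimate is an honest interval, not a test likely to succeed.

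**The case against.** The strongest reply is that this is a purpose clause in an additional analysis. Neither the aim and objectives in section 1 nor the outcome measures in section 2 mention the New Global Definition, and the verb in section 7.4 is that outcomes are reported. Read as description, the plan does what it says. That stands, and it limits the weight of the point.

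Three stronger readings are tempting, and the documents do not support them.

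- **That Berlin is left out.** It is not. Berlin strata are reported beside the New Global strata, and the whole cohort is reported too. What is missing is a specified comparison.
- **That the strata describe only the phenotype, because section 2.1 defines the primary outcome by phenotype.** Section 7.4 itself compares the primary outcome within a single phenotype, where it can only mean 60-day mortality. Even on the phenotype reading, deaths and denominators by phenotype within a grade add up to mortality per grade, for patients with a phenotype result.
- **That a Berlin-enrolled cohort can show nothing about whom another definition adds.** Section 7.4 uses the entire cohort, which includes unilateral-infiltrate AHRF and HFNO patients with assumed PEEP. It can show reclassification among those enrolled. It cannot show patients who met neither entry route.

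A further objection also stands. Restricting the whole comparison to patients gradable under both definitions would remove those on whom the definitions differ most, so the cross-tabulation must keep them.

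**Conclusion.** The point holds as a mismatch between purpose and method in a descriptive additional analysis. Sections 7.4 and 8.5 plan parallel tables and specify no cross-classification, discrimination measure or paired contrast, and no other part of the SAP supplies one. The primary analysis, the sample size and the listed secondary outcomes are unaffected, so this is an inexpensive improvement and not a serious fault.

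The conclusion rests on reading the SAP and needs no number. The two-to-threefold gain in precision depends on the assumed grade split, mortality gradient and 87–94% concordance, and on a re-draw that builds in a worse second grading. It shows scale only and does not predict which definition would do better.

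**What to change.** Replace the first paragraph of section 7.4 and the matching lines of section 8.5 with the following, for the entire study cohort.

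1. Cross-tabulate New Global category by Berlin category, with a row and a column for patients not classified or not gradable. Give 60-day mortality in each margin and in the discordant cells. State how AHRF patients are placed.
2. Report 60-day mortality per grade under each definition, phenotypes together, with 95% CIs.
3. In patients gradable under both definitions, report the paired difference in C-statistic for 60-day mortality with a bootstrap 95% CI. Label it exploratory and note that differences of about 0.02 will probably not be resolved at this sample size.

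Word the conclusion as prognostic grading and reclassification within a cohort enrolled on Berlin ARDS or unilateral-infiltrate AHRF criteria. Keep the phenotype contrasts by severity as a separate descriptive item, and add a table shell to Appendix 1.

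The cost is one paragraph of SAP text and a small extra analysis, with no new outcome. The claim becomes narrower than overall performance of the definition. If even this is not wanted, the minimum is to reword the purpose as a description of outcomes by severity under each definition.
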